Study Protocol

Effect of Citrate Dialysate on Vascular Calcification

Protocol Date: March 6, 2022

NCT04956120

PROTOCOL TITLE: Effect of Citrate Dialysate on Vascular calcification

PRINCIPAL INVESTIGATOR:

[name]
Renal Division, Department of medicine

VERSION: Version 4; 3/6/2022

FUNDING SOURCE: Fresenius Research

REVISION HISTORY

Revision #	Version Date	Summary of Changes
3	1/20/2022	Increase screening to 150
4	3/6/2022	Increase compensation to \$75

Table of Contents

1. Study Summary	4
2. Objectives.....	4
3. Background	4
4. Study Endpoints	4
5. Study Intervention/Investigational Agent	4
6. Procedures Involved.....	5
7. Data and Specimen Banking.....	6
8. Sharing of Results with Participants	6
9. Study Timelines	6
10. Inclusion and Exclusion Criteria	7
11. Vulnerable Populations	7
12. Local Number of Participants	7
13. Recruitment Methods.....	8
14. Withdrawal of Participants	8
15. Risks to Participants.....	8
16. Potential Benefits to Participants	9
17. Compensation to Participants	9
18. Data Management and Confidentiality	9
19. Provisions to Monitor the Data to Ensure the Safety of Participants.....	9
20. Provisions to Protect the Privacy Interests of Participants.....	10
21. Economic Burden to Participants	10
22. Consent Process.....	10
23. Setting.....	13
24. Resources Available	13
25. Multi-Site Research when Emory is the Lead Site	13
26. References	14

1. Study Summary

Study Title	Effect of Citrate Dialysate on Vascular calcification
Study Design	Interventional, Cross-over
Primary Objective	To determine whether dialysis with citrate reduces vascular calcification
Secondary Objective(s)	
Research Intervention(s)/Interactions	Hemodialysis with citrate dialysate or standard dialysate
Study Population	Female outpatient hemodialysis patients
Sample Size	50
Study Duration for individual participants	2 years
Study Specific Abbreviations/ Definitions	HD: hemodialysis BAC: breast arterial calcification
Funding Source (if any)	Fresenius Research

2. Objectives

To determine whether hemodialysis with citrate slows the progression of vascular calcification.

3. Background

Vascular calcification is a significant problem in dialysis patients that leads to poor outcomes (1-3). Currently there is no therapy that directly addresses this problem. Some of the dialysis solutions (dialysates) currently in use contain citrate, a potent inhibitor of calcium precipitation. In particular, citrate can bind to nascent hydroxyapatite crystals and prevent their propagation (4-5). Blood citrate levels are greater after dialysis with citrate dialysates than with non-citrate dialysates (6), which could slow vascular calcification. However, this has never been investigated. Clinical studies have been limited to the calcification propensity of serum, which decreases with citrate dialysate (7). Administration of citrate to rats with renal failure attenuated vascular calcification (8).

Our research has shown that arterial calcification can be easily detected and reliably measured on routine digital mammograms, with sufficient sensitivity to follow progression (9-13). Mammography is more sensitive in detecting arterial calcification than other imaging and associated with far less radiation and cost. This will allow us to detect differences between citrate and non-citrate dialysates in a safe and convenient way.

4. Study Endpoints

The endpoint will be the difference in the rate of progression of breast arterial calcification (BAC) between dialysis with citrate and non-citrate dialysates.

5. Study Intervention/Investigational Agent

Dialysate is generated during dialysis from two concentrates (acid concentrate and bicarbonate concentrate) mixed with treated water. When used, citrate is provided in the acid concentrate. For this study, patients will undergo hemodialysis using a citrate acid concentrate (Citrasate; Fresenius Medical Care) or non-citrate acid concentrate (Naturallyte; Fresenius Medical Care), each for one year in a cross-over study. Both acid concentrates are approved for this use by the FDA and will be used according to standard procedures without altered dialysis machine settings. Citrasate is the acid concentrate currently in use at all Emory Dialysis units and the final dialysate is pumped to each patient station from a central location. Therefore, the study intervention will be the use of Naturallyte instead of Citrasate. The Naturallyte will be ordered and stored by dialysis personnel and used by the dialysis technicians or nurses. It will be provided locally at each station as individual containers (the dialyzers are designed to use either centrally or locally supplied dialysate) so there is no risk of non-study patients receiving dialysate from Naturallyte acid concentrate.

6. Procedures Involved

Female hemodialysis patients will undergo screening mammography and those who have BAC will be enrolled. This will be a cross-over study in which half the patients will continue with citrate dialysis and the other half will be switched to non-citrate dialysis. After one year, the patients will be switch to the other dialysis. Dialysis treatments are performed 3 times per week. Mammograms will performed at 6, 12, 18 and 24 months at Emory Healthcare facilities. Patients will have monthly blood draws as part of their routine clinical care and are seen on a weekly basis by the attending nephrologist or nurse practitioner. Data to be collected during the study include:

- measurements of BAC on the mammograms (every 6 months). The mammograms will be interpreted by radiologists.
- plasma citrate, magnesium, and ionized calcium levels immediately before and after dialysis (every 6 months). These will be obtained during routine clinical blood draws and represent an insignificant amount of extra blood.
- routine blood chemistries (monthly as part of clinical protocol)
- dialysis parameters: dialysate composition, anticoagulation, body weight, ultrafiltration volume, vital signs, medications, and dialysis adequacy (automatically captured for each dialysis session in the clinical database)

Minimizing risk: Patients are routinely monitored continuously during dialysis by staff nurses and/or technicians. In addition they will be seen by nurse practitioners weekly and by attending nephrologists monthly.

Drug/device use: Naturalyte acid concentrate, which is FDA-approved for this use.

Source records/data collection: All dialysis data is automatically stored in the clinical database. Mammograms are stored in the Emory Healthcare PACS system.

Long-term follow-up: none.

7. Data and Specimen Banking

No specimens will be collected. Data will be available only to the PI and study coordinator. It will only be released to others in a de-identified form.

8. Sharing of Results with Participants

Results of the mammograms (other than the vascular calcification) will be entered in the medical record, shared with the patients, and reported to the attending nephrologist. Any suspicious findings on mammograms will be pursued per normal clinical protocol by the Breast Imaging Center, which includes contacting and educating the patient and arranging appropriate follow-up (repeat diagnostic mammograms, ultrasound, biopsy).

9. Study Timelines

Duration of an individual participant's participation in the study: 2 years.

Duration anticipated to enroll all study participants: 2 months.

Estimated date for the investigators to complete this study (complete primary analyses): 27 months.

10. Inclusion and Exclusion Criteria

Describe how individuals will be screened for eligibility: mammogram.

Inclusion criteria: adult female hemodialysis patients with BAC on mammograms.

Exclusion criteria: current warfarin use, severe hyperparathyroidism (likely to undergo parathyroidectomy in the next 2 years), difficulty controlling serum calcium (likely to require changes in dialysate calcium concentration in the next 2 years), life expectancy < 2 years, prisoners, or inability to give consent.

11. Vulnerable Populations: none

12. Local Number of Participants

Screened: 150 (estimated)

Enrolled: 124

Completed study: 50 (expected)

13. Recruitment Methods

Describe when, where, and how potential participants will be recruited: at dialysis units during dialysis sessions.

Describe the source of participants: patients undergoing chronic hemodialysis at Emory Dialysis facilities.

Describe the methods that will be used to identify potential participants: census of current dialysis patients.

Describe materials that will be used to recruit participants: none.

Describe the amount and timing of any payments to participants: \$50 for each mammogram to cover time and travel.

14. Withdrawal of Participants

Describe anticipated circumstances under which participants will be withdrawn from the research without their consent: occurrence of exclusion criteria during the study.

Describe any procedures for orderly termination. Patients will be returned to standard care.

Describe procedures that will be followed when participants withdraw from the research: no further data collection upon withdrawal; continued data collection for partial withdrawal (less frequent mammograms).

15. Risks to Participants

1. Citrate dialysis: no risks since this is the current type of dialysis.
2. Non-citrate dialysis: This is the standard type of dialysis in most units and safety is not an issue. Since the citrate dialysate may have some anticoagulant properties, changing to non-citrate dialysate may require an increase in the heparin dose given to minimize the risk of clotting of the dialysis cartridge. This is usually recognized during the dialysis session prior to clotting and is easily managed by adding additional heparin and adjusting future dosing.
3. Mammography: The radiation from a mammogram is minimal, equivalent to 7 weeks of background environmental exposure. Since most, if not all of the women would be getting annual mammograms if not in the study, the extra radiation from the 6 month

and 18 month studies would be equivalent to only 14 weeks of background environmental radiation. There is also the risk that an abnormality will be detected on the mammograms that will require further workup and may cause psychological stress. However, these abnormalities likely would be detected during clinically indicated mammography. There is some discomfort associated with mammography.

16. Potential Benefits to Participants

No direct benefit.

17. Compensation to Participants

\$75 by debit card for each mammogram.

18. Data Management and Confidentiality

Data analysis. Rate of BAC progression will be calculated by linear regression of 3 mammograms in each treatment arm: 0, 6, 12 months vs. 12, 18, 24 months. Comparison will be by paired t-testing (or Wilcoxon test in the case of nonparametric distribution). Also, the proportion of women with a decrease in BAC rate during citrate dialysis will be examined by Fisher's Exact Test. Laboratory values and dialysis parameters will be compared in patients with and without a decrease in BAC rate.

Study size. The goal is a final cohort of 50. The attrition rate among females at Emory Dialysis over the past 9 years has averaged 9.2% per year. However, this is an over-estimate since it likely includes women who would not have qualified for the study. Using a drop-out rate of 10% per year, a starting sample of 62 will be needed. Based on previous data 24, 60% of HD patients will have baseline calcification. Thus, 103 will need to be recruited and screened for BAC.

Power. Our previous studies comparing BAC rates calculated from the first 3 and last 3 mammograms (the study design for this proposal) yielded a standard deviation of 11.9 mm/breast/y. Using this value and the median BAC rate in HD patients of 20.1 mm/breast/y 27, a cohort of 47 women would provide 80% power to detect a 25% change in rate at $p=0.05$. In two longitudinal studies calculating rates from just two mammograms, we were able to detect a 78% decrease in the rate of BAC after stopping warfarin at $p=0.02$ in just 13 patients 28 and a 90% decrease after kidney transplantation in only 9 patients (unpublished data).

Subject availability. There are currently 300 female in-center HD patients within Emory Dialysis and it is estimated that at least 80% or 240 will qualify for screening. Therefore, a recruitment rate of 43% will be required. Describe the data analysis plan, including any statistical procedures or power analysis.

Data management. Data collected will be mammograms, research blood assays (citrate, magnesium, ionized calcium), clinical blood assays, and dialysis parameters. All data/specimens will be handled clinically except for samples for research assays, which will be transported to the P.I.'s laboratory by the research coordinator. Mammograms

will be stored in the Emory Healthcare PACS system, results of research blood assays will be stored in a password-protected file on a HIPAA-compliant server in the Department of Medicine, and results of clinical assays and dialysis parameters will be stored in the Emory Dialysis electronic medical record. Composite data for final analysis will be stored in a password-protected file on a HIPAA-compliant server in the Department of Medicine. Subjects will be assigned unique identifiers, the key to which will be stored as a separate, password-protected file. Access to all data will be limited to the P.I., coinvestigators, and research coordinator. Any transmitted data will not contain any identifiers. Data will be stored until all primary and secondary analyses are completed.

19. Provisions to Monitor the Data to Ensure the Safety of Participants

Patients will be monitored during each dialysis by nurses or technicians, weekly by nurse practitioners, and monthly by attending nephrologists. Clinical data (pre-dialysis labs and anticoagulation) along with intra-dialytic events are already captured per clinical protocol and stored digitally and will be reviewed monthly by the P.I. Oversight of the progress and safety of the trial will be provided by the PI. Adverse events are not anticipated, but any occurring will be documented and reported according to Emory IRB policies and procedures. Cumulative adverse events and study progress summary will be communicated to the IRB at the time of continuing review.

The only potential safety issue relates to the anticoagulant properties of citrate whereby changing to the non-citrate dialysate may increase the risk of clotting of the dialyzer (already a rare occurrence in the outpatient setting). The staff are already trained to recognize the need to increase the heparin dose prior to clotting and this is already captured on the digital dialysis records, which will be reviewed by the study team on a weekly basis for the first month for each subject. If an increased frequency of clotting or need to increase heparin dosing is noted, subsequent subjects will have their heparin dose increased pre-emptively.

Confidentiality will be protected by utilizing a code number as the only identifier for each subject and the master list will be kept under lock and key with access limited to the PI.

The PI will be responsible for reviewing protocol compliance, data collection and verification.

20. Provisions to Protect the Privacy Interests of Participants

In addition to the dialysis staff, participants will interact only with the P.I. or study coordinator. The subjects will only be asked to undergo mammograms. There will be no other intrusion of their privacy since all other data will be collected as part of their

clinical care. The P.I. will have complete access to the dialysis records and the Emory Electronic Medical Record. The study coordinator will have access to the dialysis records and will access the Emory Electronic Medical Record solely for the purpose of facilitating and monitoring the scheduling of mammograms.

21. Economic Burden to Participants

None

22. Consent Process

Indicate whether you will be obtaining consent, and if so describe:

- Where will the consent process take place? Dialysis units
- Any waiting period available between informing the prospective subject and obtaining the consent. Prospective subjects will be given up to two weeks between being informed and obtaining consent.
- Any process to ensure ongoing consent. Subjects will be informed that they can withdraw at any time.
- Please describe:
 - The role of the individuals listed in the application as being involved in the consent process. Providing information and obtaining consent.
 - The time that will be devoted to the consent discussion. As much time as the individual needs.
 - Steps that will be taken to minimize the possibility of coercion or undue influence. Potential subjects will be told that they are free not to participate and that not participating will not affect their care. The P.I. is not involved in the care of any dialysis outpatients.
 - Steps that will be taken to ensure the participants' understanding. The participants understanding will be assessed by asking them to review what they are asked to do for the study.

Non-English-Speaking Participants

- Indicate what language(s) other than English are understood by prospective participants or representatives. Primarily Spanish but could be many others.
- If participants who do not speak English will be enrolled, describe the process to ensure that the oral and written information provided to those participants will be in that language. Indicate the language that will be used by those obtaining consent. For those who do not understand English, consent will be obtained in the presence of a qualified interpreter.

Participants who are not yet adults (infants, children, teenagers) N/A

Cognitively Impaired Adults

- Describe the process to determine whether an individual is capable of consent.
Consultation with the attending nephrologist.

Adults Unable to Consent N/A

Waiver or Alteration of Consent Process (consent will not be obtained, required information will not be disclosed, or the research involves deception) N/A

23. Setting

Describe the sites or locations where your research team will conduct the research.

- Identify where your research team will identify and recruit potential participants.
Outpatient dialysis units.
- Identify where research procedures will be performed. Emory Dialysis Centers and Breast Imaging Centers
- Describe the composition and involvement of any community advisory board. N/A.

24. Resources Available

Subject availability. We will need to recruit 62 subjects to ensure a final sample of 50 allowing for 10% drop-out per year (patients dying, receiving kidney transplants, or transferring to other units). This rate has averaged 9.2% among female patients at Emory Dialysis over the past 9 years. Based on our previous data, 60% are expected to have breast arterial calcification, meaning that 103 will need to be recruited and screened for BAC. There are currently 300 female in-center HD patients within Emory Dialysis and it is estimated that at least 80% or 240 will qualify for screening. Therefore, a recruitment rate no greater than 43% will be required.

Timeline. Recruitment completed: 1 month
Last patient started: 2 months
Last patient: 26 months
Data analysis completed: 27 months

Facilities. Emory Dialysis consists of 4 large outpatient dialysis centers distributed around the Atlanta metropolitan region and is staffed by nephrologists, nurse practitioners, registered nurses, and dialysis technicians. The P.I. will work closely with the managers at each unit and hold educational meetings with staff to ensure that they are adequately informed.

The Emory Breast Imaging Center, consisting of several locations, is staffed by Emory radiologists and performs over 20,000 screening mammograms per year. Mammograms are accessible in the Emory Healthcare PACS system and reports are accessible in the Electronic Medical Record. The Center has procedures in place to contact patients about abnormal findings and discuss/arrange additional followup. The P.I. works closely with

the Medical Director ([name]), who is aware of the protocol and will be the sole radiologist interpreting the mammograms.

25. References

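### The primary paired test ignores study period in a two-order cross-over: a year-to-year change in BAC rate costs power, and biases the citrate effect if the orders finish unequal

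*Combined protocol and SAP*

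**What the plan says.** Section 5 gives each woman both dialysates, "each for one year in a cross-over study". Section 6 sets the two orders: "half the patients will continue with citrate dialysis and the other half will be switched to non-citrate dialysis", with everyone changing over after one year. Section 4 defines the endpoint as "the difference in the rate of progression of breast arterial calcification (BAC) between dialysis with citrate and non-citrate dialysates".

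Under Data analysis in section 18, each woman contributes one slope per year, by "linear regression of 3 mammograms in each treatment arm: 0, 6, 12 months vs. 12, 18, 24 months". The test follows: "Comparison will be by paired t-testing (or Wilcoxon test in the case of nonparametric distribution". Neither this section nor any other mentions a period term, an order term or a test stratified by order. The documents do not describe how women are assigned to an order.

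The Power paragraph takes its standard deviation from earlier BAC rates "calculated from the first 3 and last 3 mammograms (the study design for this proposal) yielded a standard deviation of 11.9" mm/breast/y. Section 9 adds: "Duration anticipated to enroll all study participants: 2 months".

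**The concern.** In a two-order cross-over, a change between year 1 and year 2 enters the citrate minus non-citrate difference with opposite signs in the two orders. A paired t-test pools those differences as one sample. The separation between the orders then goes into the error term and, if the orders are unequal in size, into the estimate. A signed-rank test on the same differences does not remove it either.

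Because all women start within about two months, years 1 and 2 are nearly the same calendar years for everyone. Any drift in imaging, reading or care would therefore fall on one period. At stake are the power of the only primary comparison and, if completers are unbalanced, its accuracy.

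**Working it through.** **Inputs.** From section 18: SD 11.9 mm/breast/y, median rate 20.1 mm/breast/y, a 25% change, p=0.05, 47 women for 80% power, a final cohort of 50, 62 starters and 10% drop-out per year. *Assumed:* pi, the year-2 minus year-1 change in rate, from 0 to 10 mm/breast/y. The 11.9 is read as the SD of the within-woman difference, and the test as two-sided; these readings reproduce the plan's figure.

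**The plan's own figure.** Target = 0.25 × 20.1 = 5.025. Standardised effect = 5.025/11.9 = 0.422. Noncentral t gives 80.0% at n=46, 80.9% at n=47 and 83.3% at n=50, so the stated 47 is reproduced. Drop-out: 50/0.9² = 61.7, so 62, which is also reproduced.

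**How period enters.** Let D = citrate minus non-citrate slope and tau the true effect.
- Citrate first: mean of D = tau − pi.
- Citrate second: mean of D = tau + pi.
- Pooled mean: tau + pi × (n_second − n_first)/N.
- Variance that the paired test estimates: 11.9² + 4pq × pi² × N/(N−1), where p and q are the shares in each order.

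**Equal orders (25/25).** The bias is zero and the true sampling variance of the mean is unchanged. Only the estimated standard error is too large. At pi=5 the SD used is √(141.61 + 25 × 50/49) = √167.12 = 12.93. Simulated power for a true effect of 5.025:

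| pi (mm/breast/y) | Paired test | Period-adjusted test |
|---|---|---|
| 0 | 83% | 83% |
| 4 | 80% | 83% |
| 5 | 78–79% | 83% |
| 7.5 | 73% | 83% |
| 10 | 64% | 83% |

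Type I error of the paired test is about 4.7% at pi=2, 3.3% at pi=5 and 1.1% at pi=10, so the error is on the conservative side.

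**Unequal orders, pi=5, N=50.**
- Expected gap: with 31 starting in each order and independent completion of 0.9² = 81%, the mean absolute gap is about 2.4. Bias = 5 × 2.4/50 = 0.24, and 0.24/5.025 = 5% of the target.
- 22/28: 5 × 6/50 = 0.60, or 12%. A gap of 6 or more has probability about 7%.
- 20/30: 5 × 10/50 = 1.0, or 20%, with type I error about 6.6%. A gap of 10 or more has probability about 0.2%.

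The direction depends on which order is larger. If rates rise in year 2 and more women complete citrate second, a benefit of citrate is understated. With the reverse split it is overstated. At 22/28, power is about 67% in the first case and 87% in the second.

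**Period-adjusted test.** Standard error = (11.9/2) × √(1/n_A + 1/n_B), on N−2 degrees of freedom. Power is 83.3% at 25/25, 82.8% at 22/28, 81.8% at 20/30 and 80.8% with 47 women, whatever pi is, with no bias and type I error of 5%.

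**The case against.** The strongest reply is that the harm is small in the setting the plan describes. With equal halves, pi cancels from the mean and the test errs on the safe side. The planned 50 completers leave a margin over 47, so 80% power survives pi up to about 4 mm/breast/y, a 20% shift in the median rate (4/20.1). Section 24 lists death, transplant and transfer as the causes of drop-out, and nothing suggests that these differ by order. It also names a sole radiologist for all readings, which limits reader drift, although section 6 speaks of radiologists in the plural. All of this stands and sets the severity. It does not show that pi is zero, nor does it secure equal halves, because assignment to order is not described.

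A reader might infer four stronger points that the documents do not support:

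- *That the stated power holds only without a period effect.* At 50 completers this is not so, as the table shows.
- *That the SD of 11.9 excludes a mean shift between periods.* The plan does not say exactly what it is the SD of, and the earlier studies are not available.
- *That selecting women on a positive screening mammogram distorts the year-1 slope.* Eligibility requires only that BAC be present, which is expected in 60%. No size or direction can be derived.
- *That the months listed in the analysis sentence make the test a year-1 versus year-2 contrast.* The same sentence speaks of treatment arms, and section 4 makes the citrate versus non-citrate contrast clear.

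**Conclusion.** The concern holds as a matter of efficiency, with a limited risk of bias. The paired test leaves out a term that the design calls for. At 25/25 completers it costs about 3 power points at pi=4, 4 to 5 at pi=5 and 19 at pi=10. Bias at pi=5 is about 5% of the target for the expected gap and 12% at 22/28. The 20% figure needs a 20/30 split, which is very unlikely if the orders start equal and drop out alike; the documents do not secure either condition.

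All of these sizes rest on assumed values of pi and on 11.9 being the SD of the within-woman difference. A shift of 10% of the median rate (2.01) with equal orders costs under 1 point. This is a should-fix, not a must-fix: a reader might conclude that the primary test is invalid, but with equal or mildly unequal orders it is conservative.

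**What to change.** Replace the paired test in section 18 with a period-adjusted cross-over analysis. For each woman take the period 1 minus period 2 slope. Estimate citrate minus non-citrate as half the difference in its mean between the citrate-first and citrate-second groups, tested by a two-sample t-test (Hills-Armitage). The non-parametric version is the rank-sum test on the same period differences. An equivalent mixed model with fixed treatment and period effects would also serve.

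State in the same place how women are assigned to an order. The adjustment assumes that the year-to-year change is the same in both orders, and comparable groups are what support that assumption.

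The cost is a sentence or two and one degree of freedom: under 0.1 power point at 25/25 if pi is zero, and about 1.5 points at 20/30 (83.3% − 81.8%). No new data or extra women are needed, and 47 women still give 80% power. The change should be made before the data are seen, because a later choice to adjust for period would be open to challenge.

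### Fisher's exact test is named for a single within-woman proportion, with no comparison group, table or null value, so the test does not fit the quantity described

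*Combined protocol and SAP*

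**What the plan says.** Section 5 describes treatment with the two acid concentrates "each for one year in a cross-over study". Section 6 sets up the two sequences: "half the patients will continue with citrate dialysis and the other half will be switched to non-citrate dialysis", with a switch after a year. Every completer therefore has a BAC rate on each dialysate.

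Section 18 (Data analysis) fits a slope to three mammograms per period and treats the two slopes as a pair: "Comparison will be by paired t-testing (or Wilcoxon test in the case of nonparametric distribution"). It then adds that "the proportion of women with a decrease in BAC rate during citrate dialysis will be examined by Fisher's Exact Test". No comparator, cross-tabulation or reference value accompanies that sentence. The next one reuses the same split: "Laboratory values and dialysis parameters will be compared in patients with and without a decrease in BAC rate".

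Section 4 names one endpoint, the difference in progression rate. The secondary-objective row in section 1 is blank. The Fisher analysis is thus an addition to the main comparison, and the power paragraph does not cover it.

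**The concern.** Whether a woman's rate was lower on citrate is a single binary result that already contains her comparison between treatments. Across the cohort these results form one proportion, and the natural null value is 50%. Fisher's test needs a second, independent group, and the sentence supplies none. The analyst would have to invent a table, possibly after seeing the data.

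The candidate tables differ in type I error and even in the question they answer. A count such as 31 of 50 could be reported as significant or not, depending on an unstated choice. At stake is the credibility of any statement about how many women did better on citrate.

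**Working it through.** **Inputs**
- Completers: 50 (section 18, Study size: "The goal is a final cohort of 50").
- Sequence groups: 25 and 25, from the half-and-half split in section 6, assumed to hold among completers.
- Reference rate 20.1 mm/breast/y, 25% change, 80% power, p = 0.05, 47 women (section 18, Power). The earlier comparison of rates "yielded a standard deviation of 11.9 mm/breast/y".
- Assumptions: two-sided tests; 11.9 is the SD of the within-woman difference; differences are normal; no ties.

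**The plan's own figure**

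The difference to detect is 0.25 × 20.1 = 5.025. The normal formula gives [11.9 × (1.960 + 0.842) / 5.025]² = 44.0, so 45 women. With the exact noncentral t, 46 women give 80.0% power and 47 give 80.9%. The stated 47 reproduces to within two women, which supports reading 11.9 as the SD of the paired difference.

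**Chance that a woman is lower on citrate**

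Under the plan's effect with no period effect: Φ(5.025/11.9) = Φ(0.422) = 0.664. Under no effect: 0.5.

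**Reading 1: the mirrored table**

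Let X be the number lower on citrate. The rows are (X, 50−X) and (50−X, X), treated as two groups of 50. The second row is fixed by the first. The difference in proportions is 2X/50 − 1. Its true SD under the null is 2√(0.25/50) = 0.141, whereas two independent groups of 50 would give √(2 × 0.25/50) = 0.100.

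| X of 50 | Fisher p, mirrored table | Exact sign-test p |
|---|---|---|
| 30 | 0.071 | 0.203 |
| 31 | 0.027 | 0.119 |
| 32 | 0.009 | 0.065 |
| 33 | 0.003 | 0.033 |

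Fisher's test rejects at X ≥ 31 or X ≤ 19. Summing Binomial(50, 0.5) over that region gives 11.9%. The same enumeration gives 14.4% at 47 women, and 9.6% to 16.4% over 40 to 62 women.

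**Reading 2: decrease on citrate (yes/no) by sequence group, 25 against 25**
- Citrate effect 5.025, no period effect: both groups have probability 0.664, and the test rejects 2.5% of the time.
- No citrate effect, period effect 5.025: the probabilities are 0.664 and 0.336, and the test rejects 58.7% of the time.

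This table responds to period and is blind to citrate.

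**Other layouts, and the replacement**

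| Analysis, n = 50 | Type I error, no effects | Rejection, citrate effect only | Rejection, period effect only |
|---|---|---|---|
| Mirrored Fisher | 11.9% | 79.0% | 9.9% |
| Decrease by sequence | 3.3% | 2.5% | 58.7% |
| X/50 against a notional 25/50 | 0.3% | not calculated | not calculated |
| Mainland-Gart (sequence by period with the lower rate) | 3.3% | 58.7% | 2.5% |
| Exact sign test against 50% | 3.3% | 58.7% | 2.4% |

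The sign test rejects at X ≥ 33 or X ≤ 17. The notional comparator rejects only from 36 women upwards.

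**The case against.** The best defence is that the sentence fixes no table, so it cannot be said to require a bad one. A cross-over does contain two independent groups, the two sequences. Tabulating sequence against the period with the lower rate gives a proper Fisher test of citrate, with the same size and power as the sign test. Comparing against a notional 25 of 50 errs on the cautious side. This part stands: a reader might infer that Fisher's test must either inflate the error rate or test order, and that is not so. Nor does the plan say that women will be counted twice, so the 12% belongs to one layout at one sample size.

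What does not stand is that this makes the sentence adequate. The quantity it names is a decrease during citrate. The Mainland-Gart table needs a different outcome, lower in period 1 or period 2, which the plan nowhere describes.

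The defence is also right about scope. The analysis supplements a comparison that respects the pairing, and no sample size rests on it.

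A reader might further infer that the laboratory and dialysis comparison sets apart groups formed mainly by noise. If every woman had exactly a 25% reduction and 11.9 were the SD of the within-woman difference, (1 − 0.664) × 50 = 16.8, about 17 of 50 women, would still show no decrease. That assumes a uniform effect. The documents do not divide 11.9 between measurement error and real variation in response, so the figure illustrates a scenario and does not show that the split is mostly noise.

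**Conclusion.** The point holds as a mismatch between test and quantity. A two-group test is assigned to one within-woman proportion, with no second group, table or null value. The two most literal readings give either 11.9% type I error at 50 completers (14.4% at 47) or a test of period with 2.5% rejection under the plan's own effect. These figures assume two-sided testing at 0.05, no ties and, for the second, 25 women per sequence and normal differences with SD 11.9.

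Severity is moderate. It would be tempting to conclude that the trial's main result is at risk, but the documents do not support that: the paired t or Wilcoxon comparison and the stated 47 women are unaffected.

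**What to change.** In section 18, replace Fisher's test with an exact binomial (sign) test of the proportion of women whose rate is lower on citrate, against 50%, with an exact 95% confidence interval. State how ties are handled. Alternatively, keep Fisher's test but specify the Mainland-Gart table: sequence group by which period had the lower rate. This second form is preferable if a period effect is plausible and drop-out may leave the sequences unequal, because the null proportion for the sign test need not then be 50%.

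Either test has about 59% power at the plan's effect, against 83% for the paired t-test with 50 women. The proportion should therefore be labelled supplementary, and a non-significant result should not be read as evidence of no effect.

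Optionally, and as a matter of efficiency only, relate laboratory values and dialysis parameters to each woman's slope difference (citrate minus non-citrate) as a continuous outcome, using her within-woman differences in those measures, in place of the decrease/no-decrease split.

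The cost is one or two sentences of analysis text. No extra data, visits or participants are needed.
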